3.3. Inclusion of Women and Minorities

Both men and women and members of all races and ethnic groups are eligible for this trial. Below is an estimate of expected accrual targets for this trial.

3.4. Accrual Targets

Ethnic Category	Sex/Gender				
	Females		Males		Total
Hispanic or Latino	8	+	8	=	16
Not Hispanic or Latino	47	+	47	=	94
Ethnic Category: Total of all subjects	55	+	55	=	110
Racial Category					
American Indian or Alaskan Native	2	+	2	=	4
Asian	2	+	2	=	4
Black or African American	7	+	7	=	14
Native Hawaiian or other Pacific Islander	2	+	2	=	4
White	42	+	42	=	84
Racial Category: Total of all subjects	55	+	55	=	110

4. REGISTRATION PROCEDURES

4.1. General Guidelines

Eligible patients will be entered on study centrally at the University of Chicago by the Study Registrar. All sites should call the Study Registrar at **[contact]** or **[contact]**, to verify agent availability. The UC

Phase II Consortium Affiliate Forms are available on the University of Chicago Cancer Research Center website.

- <http://uccrc.uchicago.edu/current/home.html>
- Click on the **Staff Resources** link and scroll down to “UC Phase II Consortium Forms” section.

Except in very unusual circumstances, each participating institution will order DCTD-supplied agents directly from CTEP. Agents may be ordered by a participating site only after the initial IRB approval for the site has been forwarded by the Coordinating Center to the CTEP PIO ([contact]) except for Group studies. Eligible patients will be entered on study centrally at the University of Chicago by the Registrar. All sites should call the Registrar at [contact] to verify agent availability.

Following registration, patients should begin protocol treatment within 14 days. Issues that would cause treatment delays should be discussed with the Principal Investigator. If a patient does not receive protocol therapy following registration, the patient’s registration on the study may be canceled. The Registrar should be notified of cancellations as soon as possible.

4.2. Registration Process

All patients must be registered with the University of Chicago Registrar at least 48 hours prior to the commencement of treatment. The following documents should be completed by the research nurse or data manager and faxed [contact] or emailed [contact] to the Registrar:

- Provider of information
- Treating Physician
- Patient name and hospital ID number
- Patient's zip code of residence
- Date & copy of signed informed consent
- Race, gender, date of birth of patient
- Diagnosis and date of initial diagnosis
- Prior therapy with a VEGF-pathway inhibitor (yes/no)
- ECOG performance status
- Complete **Phase II Consortium Affiliate Clinical Trial Patient Registration Form**
- Source documentation for eligibility and pre-study procedures

The research nurse or data manager at the participating site will then call [contact]) or e-mail [contact] to confirm all selection criteria listed in Section 4.0. To complete the registration process, the Coordinator will:

- Assign a patient study number
- Register the patient on the study
- Fax or e-mail the patient study number and dose to the participating site

Call the research nurse or data manager at the participating site and verbally confirm registration.

Each site must have two trained counselors available for counseling all patients receiving lenalidomide supplied by the Division of Cancer Treatment and Diagnosis. Trained counselors must complete training using the online program provided free by Celgene, the Lenalidomide Counseling Program (LCP). Registration for LCP is done by completing the form found in Appendix K and following the directions provided in the email notification. After the training is complete, the counselors must generate a training certificate and provide it to the PMB for documentation. Sites may not order lenalidomide until documentation for two trained counselors is provided to the appropriate office.

5. TREATMENT PLAN

5.1. Agent Administration

Treatment will be administered on an outpatient basis. Cediranib tablets should be taken either 1 hour before or 2 hours after meals. Cediranib will be taken daily on a continuous basis for each 28 day cycle. If a dose of cediranib is missed, it should be taken as soon as possible on the same day. If it is missed for the entire day, it should not be made up. Lenalidomide will either be taken for 21 days of the 28 day cycle or daily, depending on the level of dose escalation. Lenalidomide can be taken with or without food. Lenalidomide capsules should be swallowed whole, and should not be broken, chewed or opened. If a dose of lenalidomide is missed, it should be taken as soon as possible on the same day. If it is missed for the entire day, it should not be made up. Patients who take more than the prescribed dose of lenalidomide should be instructed to seek emergency medical care if needed and contact study staff immediately.

Lenalidomide capsules should be swallowed whole. For patients who are unable to swallow lenalidomide whole, lenalidomide can be administered via gastrostomy feeding tube following the instructions in Appendix M.

For patients who are unable to swallow cediranib tablets, cediranib tablets may be administered as a dispersion in water (ie, either drinking water, sterile water [for injection] or purified water). The following procedure is recommended:

Cediranib tablets may be dispersed in half a glass (2 fluid ounces or 50 ml) of non-carbonated drinking water. No other liquids should be used. The tablet is dropped in water, without crushing, stirred until dispersed (approximately 10 minutes) and the resultant dispersion swallowed immediately. Any residues in the glass are mixed with half a glass of

water and swallowed. The liquid can also be administered through nasogastric or gastrostomy tubes. Where patients require the dose to be administered by nasogastric or gastrostomy tubes, cediranib tablet(s) dispersed in water can be dosed with: Polyurethane (PUR) or Poly vinylchloride (PVC) naso-gastric, naso-intestinal or percutaneous endoscopic gastrostomy (PEG) feeding systems in conjunction with PUR syringes. PVC syringes are not recommended for use. Two system washes are conducted through the giving set to ensure the correct dose is obtained.

Only one cycle of therapy may be dispensed to the patient each month.

Dose modification for Phase I study	Cediranib + Lenalidomide
-1	Cediranib 20 mg (28/28 days) + Lenalidomide 10 mg (21/28 days)
0	Cediranib 20 mg (28/28 days) + Lenalidomide 15 mg (21/28 days)
+1	Cediranib 30 mg (28/28 days) + Lenalidomide 15 mg (21/28 days)
+2	Cediranib 30 mg (28/28 days) + Lenalidomide 15 mg (28/28 days)
+3	Cediranib 30 mg (28/28 days) + Lenalidomide 20 mg (21/28 days)
+4	Cediranib 30 mg (28/28 days) + Lenalidomide 20 mg (28/28 days)

Number of Patients with DLT at a Given Dose Level	Escalation Decision Rule
0 out of 3	Enter 3 patients at the next dose level
> 2	Dose escalation will be stopped. This dose level will be declared the maximally administered dose (highest dose administered). Three (3) additional patients will be entered at the next lowest dose level if only 3 patients were treated previously at that dose.
1 out of 3	Enter at least 3 more patients at this dose level. If 0 of these 3 patients experience DLT, proceed to the next dose level. If 1 or more of this group suffer DLT, then dose escalation is stopped, and this dose is declared the maximally administered dose. Three (3) additional patients will be entered at the next lowest dose level if only 3 patients were treated previously at that dose.
≤1 out of 6 at highest dose level below the maximally administered dose	This is generally the recommended phase 2 dose. At least 6 patients must be entered at the recommended phase 2 dose.

Dose Limiting Toxicity (DLT) will be determined during the first cycle for dose escalation. Toxicity occurring in subsequent cycles will not be considered dose limiting but will require dose modification. (See Section 6.0 for Dose Modification)

DLT will be defined as follows:

- Hematological toxicities:
 - Any grade 4 neutropenia (ANC < 500) lasting more than 5 days
 - Any grade 4 neutropenia with concomitant fever (temperature > 38.5)
 - Any grade 4 neutropenia and sepsis or other severe infection
 - Any grade 4 thrombocytopenia
- Any other grade 3-4 non-hematological adverse drug reactions, except untreated nausea/vomiting, or hypersensitivity reactions.
- Grade 4 hypertension
- Grade 4 proteinuria
- Delay in the administration of a subsequent dose of cediranib and lenalidomide exceeding 2 weeks, due to an adverse drug reaction.

For patients in the Phase I trial, disease re-evaluation will occur every 8 weeks using

RECIST guidelines.* Patients without evidence of anti-thyroglobulin antibodies will continue to have thyroglobulin levels measured at each response assessment (usually every 8 weeks). All patients are expected to be on thyroxine suppression therapy and thyroid stimulation hormone (TSH) levels will be monitored pre-therapy and every 8 weeks during therapy.

*After 18 cycles, radiologic disease re-evaluation will occur every 16 weeks.

Phase I toxicity: In the Phase I study, of 15 evaluable patients, 4 were enrolled at the starting dose (cediranib 20 mg daily with lenalidomide 15 mg on days 1- 21 of 28 days), 6 were enrolled in the +1 dose modification, 5 in the + 2 dose modification. DLTs in the +2 dose modification were Grade 3 fatigue and Grade 3 mucocitis. The DLT in the +1 modification was Grade 3 fatigue. Since 1 of 6 patients in the +1 group (cediranib 30 mg daily and lenalidomide 15 mg on day 1-21,) this was determined to be the starting dose for the Phase II trial.

5.1.2. Cediranib and lenalidomide administration

Please note, as of **April 10, 2015**, patients assigned to Arm B (Combination of cediranib and lenalidomide) are to discontinue lenalidomide and may continue on cediranib alone.

After determining the MTD or reaching the maximum dose specified above of cediranib with lenalidomide in the Phase I portion of this study, the Phase II study will be initiated.

Subjects will be randomized in a 1:2 ratio to one of two arms. Randomized stratification will employ prior therapy with a VEGF-pathway inhibitor (yes vs. no) and performance status (0 and 1 vs. 2). In Cohort A, subjects (n = 36) will receive cediranib alone at 30 mg daily. In Cohort B, subjects (n = 74) will receive cediranib and lenalidomide at the dose determined in the Phase I study. Each cycle will be 4 weeks in length. Disease re-evaluation will occur every 8 weeks using RECIST guidelines. After 18 cycles, disease re-evaluation will occur every 16 weeks. Patients without evidence of anti-thyroglobulin antibodies will continue to have thyroglobulin levels measured at each response assessment (usually every 8 weeks). All patients are expected to be on thyroxine suppression therapy and thyroid stimulation hormone (TSH) levels will be monitored pre-therapy and every 8 weeks during therapy.

- Patients will take cediranib or cediranib and lenalidomide. Cediranib will be taken daily at 30 mg. Lenalidomide will be taken on day 1-21 of the 28 day cycle at 15 mg. Proper administration of cediranib and lenalidomide is described in Section 5.1. A 4-week period constitutes one cycle of treatment.
- Patients will be provided with a Medication Diary for cediranib and lenalidomide (Appendix B), instructed in its use, and asked to bring the diary with them to each

appointment. A new copy of the Medication Diary will be given to patients each cycle and for those whose dose is reduced due to adverse events.

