1.3. Secondary Objectives

- Determine response rates and duration of response, early tumor size changes, the toxicity, and overall survival in patients with DTC treated with cediranib or cediranib plus lenalidomide.
- Determine whether the presence of *B-RAF* or *K-RAS* mutations in patients with DTC predict response to cediranib or cediranib plus lenalidomide.

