5.3. Duration of Therapy

In the absence of treatment delays due to adverse event(s), treatment may continue until one of the following criteria applies:

- Disease progression,
- Intercurrent illness that prevents further administration of treatment,

- Unacceptable adverse events(s),
- Patient decides to withdraw from the study, or
- General or specific changes in the patient's condition render the patient unacceptable for further treatment in the judgment of the investigator.

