5.4. Duration of Follow Up

Patients removed from study for unacceptable adverse events will be followed until resolution or stabilization of the adverse event. Unless the patient withdraws from the study, the subject will be followed until disease progression or death, whichever comes first.

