7.5. Routine Adverse Event Reporting

All Adverse Events **must** be reported in routine study data submissions. **AEs reported through CTEP-AERS must also be reported in routine study data submissions.**

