11.1.6. Progression-Free Survival

Progression free survival (PFS) is defined as the duration of time from start of treatment to time of progression or death of any cause.

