13.4. Analysis of Secondary Endpoints

13.4.1. Phase I.

The objective response rate of cediranib in combination with lenalidomide in patients with iodine refractory, unresectable DTC who have evidence of disease progression within 6 months of study enrollment will be estimated. In addition, the toxicity, duration of response, progression free survival, and overall survival in patients with DTC treated with cediranib plus lenalidomide will be evaluated.

13.4.2. Phase II.

Overall survival (OS) rates will be estimated and compared between groups using methods similar to that described above for PFS. Response rates will be compared using a chisquare test followed by logistic regression analysis to adjust for covariates.

The percent change in tumor size from baseline to the end of cycle 2 (two months) will be compared between the two groups using a two-sample t test³³. The post-treatment total sum of lengths for a patient with a new lesion will be scored as $1.2 * \max(\text{pre-sum}, \text{post-sum})$ to ensure that the appearance of new lesions corresponds to a disease progression per RECIST criteria. In the event of any early deaths prior to two months, a nonparametric rank sum test will be used in place of the t test, with deaths ranked at the extreme end of the distribution.

Adverse events will be summarized by type and grade. Adverse event rates will be compared between the two treatment groups using a chisquare test for common toxicities and Fisher's exact test for less frequent events.

Repeated measures analysis of variance (RM ANOVA) will be performed to determine the effect of the treatments on serial measurements of TSH and thyroglobulin. It is hypothesized that these levels will decrease over time. Baseline tissue biomarker expression, scored as present or absent, of *B-RAF* and *RAS* mutations will be correlated with response rates using Fisher's exact test, and with PFS and OS by fitting a Cox proportional hazards regression model.

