13.5. Reporting and Exclusions

13.5.1. **Evaluation of toxicity.** All patients (Phase I and II) will be evaluable for toxicity from the time of their first treatment with cediranib or cediranib plus lenalidomide.

13.5.2. **Evaluation of response.** All patients included in the study (Phase I and II) will be assessed for response to treatment, even if there are major protocol treatment deviations or if they are ineligible. Each patient will be assigned one of the following categories: 1) complete response, 2) partial response, 3) stable disease, 4) progressive disease, 5) early

death from malignant disease, 6) early death from toxicity, 7) early death because of other cause, or 9) unknown (not assessable, insufficient data).

All of the patients who met the eligibility criteria (with the possible exception of those who received no study medication) will be included in the main analysis of the response rate. Patients in response categories 4-9 will be considered to have a treatment failure (disease progression). Thus, an incorrect treatment schedule or drug administration will not result in exclusion from the analysis of the response rate.

All conclusions will be based on all eligible patients. Subanalyses may then be performed on the basis of a subset of patients, excluding those for whom major protocol deviations have been identified (e.g., early death due to other reasons, early discontinuation of treatment, major protocol violations, etc.). However, these subanalyses will not serve as the basis for drawing conclusions concerning treatment efficacy, and the reasons for excluding patients from the analysis will be clearly reported. Data will be reported to CTEP using CDUS -Complete.

REFERENCES

1. National Cancer Institute. Surveillance, Epidemiology, and End Results (SEER) Program. <http://seer.cancer.gov/> Accessed 2009.
2. American Cancer Society. www.cancer.org/docroot/home/. Accessed 2009.

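### Does the 10 April 2015 lenalidomide stop in Arm B call for a change to the Section 13 analyses?

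*Combined protocol and SAP*

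**What the plan says.** Section 5.1.2 states that, as of 10 April 2015, "patients assigned to Arm B (Combination of cediranib and lenalidomide) are to discontinue lenalidomide and may continue on cediranib alone". The schema and Section 8.1.3 repeat that Arm B no longer receives lenalidomide. The amendment log places the change in Amendments 27 (December 2016) and 28 (January 2017) and lists no edit to Section 13.

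For PFS, Section 11.1.6 counts the "duration of time from start of treatment to time of progression or death of any cause". Section 5.4 adds: "Unless the patient withdraws from the study, the subject will be followed until disease progression or death, whichever comes first". Section 13.1.2 compares the arms by stratified logrank test, with 1 year of accrual, 1.5 years of further follow-up and 80 projected events.

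For AEs, Section 13.4.2 says: "Adverse event rates will be compared between the two treatment groups using a chisquare test for common toxicities", with Fisher's exact test for rarer events. Section 13.5.1 says that patients "will be evaluable for toxicity from the time of their first treatment with cediranib or cediranib plus lenalidomide", and names no end date. Section 7.5 requires all AEs to "be reported in routine study data submissions". Section 1.3 lists among its objectives "the toxicity, and overall survival in patients with DTC treated with cediranib or cediranib plus lenalidomide".

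**The concern.** Under Section 5.3, "treatment may continue until one of the following criteria applies", the main one being progression. Some Arm B patients could therefore have been on cediranib alone for months after the stop. Followed literally, Sections 13.4.2 and 13.5.1 count an event in that period under the combination arm, although the objective is to describe toxicity on each regimen. For PFS, events after the stop stay in Arm B. If the benefit of lenalidomide ended with the drug, those events would pull the hazard ratio toward 1. Section 13 neither says that the comparison disregards the stop nor gives a calendar cut-off. A reader of this open-label trial might then be unsure whether the hazard ratio describes the combination as given or the randomised strategy including the stop.

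**Working it through.** **1. The plan's own figures.** Inputs from Section 13.1.2: one-sided alpha 0.10, 85% power, HR 1.75, medians 40 and 70 weeks, 36 and 74 patients.

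- Schoenfeld events: (1.2816 + 1.0364)² / [(36/110)(74/110)(ln 1.75)²] = 77.9, so 78 against 80 stated.
- Power at 80 events: Φ(√(80 × 0.3273 × 0.6727) × 0.5596 − 1.2816) = 0.857.
- Expected events from exponential PFS, 52.18 weeks of uniform accrual and 78.27 weeks of follow-up: 29.9 + 47.4 = 77.3.

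The design reproduces.

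**2. Planned timetable.** The documents give no accrual dates. Assume a start on 9 April 2012, the date of Amendment 14, which made PFS the primary endpoint. Adding 2.5 years gives about October 2014, some six months before the stop. No PFS event, and no AE at the same lock, then falls after it.

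**3. Arm B patients possibly still on drug at the stop, if treatment and data collection ran on.** Let λ = ln 2/70, d = the weekly rate of leaving treatment for other reasons, and k = λ + d. With time from randomisation to the stop uniform between a and b weeks, the count is 74 × [exp(−ka) − exp(−kb)] / [k(b − a)].

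| Accrual (assumed) | a, b | d = 0 | d = ln 2/140 | d = ln 2/70 |
|---|---|---|---|---|
| Apr 2012–Apr 2013 | 104.4, 156.6 | 20.6 | 10.9 | 5.8 |
| Apr 2012–May 2014 | 46.4, 156.6 | 28.4 | 18.3 | 12.0 |

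May 2014 is the date of Amendment 22, which added a sub-site.

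**4. Effect on the planned AE tests.** Chi-square and Fisher tests use the proportion of patients with an event, so what matters is a first event that occurs only after the stop. Assume r = 0.1 to 0.3 AEs per patient-year on cediranib (converted to a weekly rate in the formula), once or twice that on the combination (r_c), d = ln 2/140, 104 further weeks of data, and a PFS hazard that reverts to ln 2/40 after the stop. Per patient, the probability is

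mean of exp(−(λ + d + r_c)u) × r/h × (1 − exp(−104h)), with h = ln 2/40 + d + r.

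- Accrual to April 2013: 0.5 to 1.0 of 74 patients.
- Accrual to May 2014: 1.0 to 2.2 of 74, that is 1.3 to 2.9%.
- Accrual stretched to October 2014, which no accrual record supports: up to 2.9 of 74, or 3.9%.

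Arm A also gains first events over the same period. The same formula with its own hazard gives, in the largest May 2014 case, 2.9% in Arm B and 1.6% in Arm A, a shift of 1.3 percentage points in the difference. The October 2014 case gives 3.9% and 2.5%, a shift of 1.4 points. The corresponding change in chi-square power is about 2 points.

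**5. PFS under slower accrual.** These are 4,000 simulated trials per scenario with an unstratified logrank test (Monte Carlo SE 0.005 to 0.007) and accrual from April 2012 to May 2014. Each cell shows power for the by-arm analysis, then for a common cut-off at the stop.

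| Benefit after the stop | Analysed at 80 events | Analysed at the later of 80 events and accrual end + 78 weeks |
|---|---|---|
| Ends | 0.842, 0.856 | 0.818, 0.853 |
| Half persists | 0.852, 0.848 | 0.856, 0.849 |
| All persists | 0.866, 0.852 | 0.879, 0.852 |

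In the benefit-ends case analysed at 80 events, about 6 events (80 − 74.1) come after the stop. The cut-off gains 1.4 to 3.5 points if the benefit ends, is about neutral if half persists, and loses 1.4 to 2.7 points if all persists.

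**The case for a change.** The strongest contrary case is that the omission is real and the remedy is only text. Sites were still being added in July 2013 and January 2014, and a sub-site in May 2014, so accrual may well have run past the planned year. If accrual took three years from April 2012 and the analysis came 1.5 years later, about 43% of Arm B events would follow the stop. If the benefit also ended then, simulated power would be 0.69 by arm against 0.80 with a cut-off at the stop.

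The omission stands, and slower accrual is plausible. But the three-year case joins two assumptions that the documents do not establish, and the cut-off would be post hoc because the stop entered the protocol only in December 2016. Even there the by-arm test loses power without losing validity.

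A second argument is that AE rates per unit of treatment time would be diluted. Section 13.4.2 plans no such rates. Nor do the documents show that the AE comparison is locked later than PFS, so counting post-stop AEs with the combination is a possibility and not an established result.

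**Conclusion.** No change to the plan is needed. Read together, Sections 11.1.6, 5.4 and 13.1.2 leave every PFS event in its assigned arm, which is a treatment-policy handling of the stop in all but name. That label applies to the stop only, since PFS starts at treatment and Section 13.5.2 bases conclusions on eligible patients. Timing is set by 80 projected events and a 2.5-year duration, so the absence of a calendar date is not a defect. No stated figure changes.

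The effect is nil if the planned timetable ran from April 2012. With a later lock it is about 0.5 to 2.2 first AEs among 74 Arm B patients (2.9 at the outer bound) and a shift of no more than about 1.5 points in the between-arm difference. The consequence for PFS power depends on how much benefit outlasted the drug. All of this rests on assumed accrual dates, exponential PFS with the design medians, and assumed AE and discontinuation rates.

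Analysts would sensibly report the lock date relative to 10 April 2015. If the lock is later, they would show Arm B AEs after the stop separately, and would present any analysis cut at that date in both arms as post hoc and supportive.
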